8.4. Unscheduled Visits

All attempts should be made to keep subjects on the study schedule. If disease activity increases or other concerns arise between regularly scheduled visits, participants should be instructed to contact study personnel and may be asked to return to the study site for an “unscheduled” visit.

Unscheduled visits may be performed for significant food allergy episodes which may be reported by the subject between regularly scheduled visits. Unscheduled visits may include, but are not limited to, physical examination, lung function testing, and in-clinic OIT dosing. Review of the

circumstances surrounding the episode and appropriate documentation of the AE will be recorded in the study chart.

8.5. Early Termination Visit

Subjects who are withdrawn from the study prior to study completion (completion of both week 24 DBPCFC visits) will be asked to return to the clinic for an Early Termination visit within 14 days of the last dose of the study drug consisting of end-of-study assessments. This visit may include a blood draw for immunological parameters and translational/mechanistic studies; stool/saliva sampling; and/or physical exam, spirometry (as able), and skin testing.

8.6. Schedule of Events

Study assessments and procedures are presented by study period and visit in **Table 4**.

Table 4: Schedule of Events

Study Procedure	Screening	Active Run-In Phase (Dupilumab/Placebo)		Combination Therapy Phase (Dupilumab/Placebo + Milk Protein OIT)							Washout Phase (Milk Protein OIT)						
		V2	V3 ²	V4	V5	V6	V7	V8	V9	V10	V11a	V11b ³	V12 ⁴	V13	V14a	V14b ⁵	
Visit (V)	V1 ¹																
Week (W)	Within 6 months of V2 ⁶	W0	W2	W4	W6	W8	W10	W12	W14	W16	W18a	W18b	W20	W22	W24a	W24b	
Visit Window (d)	NA	±5d	±5d	±5d	±5d	±5d	±5d	±5d	±5d	±5d	±5d	V11a + 7d	±5d	±5d	±5d	V14a + 10d	
Informed Consent/Assent ⁷	X																
Inclusion/Exclusion	X	X															
Medical History/ Demographics	X																
Height/Weight ⁸	X	X	X	X	X	X	X	X	X	X	X	X	X	X	X	X	
Vital Signs ^{8,9}	X	X	X	X	X	X	X	X	X	X	X	X	X	X	X	X	
Physical Examination ⁸	X	X	X	X	X	X	X	X	X	X	X	X	X	X	X	X	
Lung Function ^{8,10}	X	X	X	X	X	X	X	X	X	X	X	X	X	X	X	X	
Urine Pregnancy Test ⁸	X	X	X	X	X	X	X	X	X	X	X	X	X	X	X	X	
DBPCFC	X ¹¹										X	X				X	X
Milk Skin Prick Test	X ¹²	X									X					X	
Blood Draw (Mechanistic) ^{8,13}		X		X							X					X	
Stool/Saliva (Optional) ⁸		X														X	
Randomization		X															
Epinephrine Auto-injector Training	X			X													
Daily Dosing & Symptom Diary Training		X		X													
Subject Dosing & Symptom Diary Review ⁸			X	X	X	X	X	X	X	X	X	X	X	X	X	X	
Blinded Study Drug Administration ¹⁴		X	X	X	X	X	X	X	X	X							
Adverse Events	X	X	X	X	X	X	X	X	X	X	X	X	X	X	X	X	
Con Meds	X	X	X	X	X	X	X	X	X	X	X	X	X	X	X	X	

Study Procedure	Screening	Active Run-In Phase (Dupilumab/Placebo)		Combination Therapy Phase (Dupilumab/Placebo + Milk Protein OIT)							Washout Phase (Milk Protein OIT)						
		V1 ¹	V2	V3 ²	V4	V5	V6	V7	V8	V9	V10	V11a	V11b ³	V12 ⁴	V13	V14a	V14b ⁵
Visit (V)	V1 ¹	V2	V3 ²	V4	V5	V6	V7	V8	V9	V10	V11a	V11b ³	V12 ⁴	V13	V14a	V14b ⁵	
Week (W)	Within 6 months of V2 ⁶	W0	W2	W4	W6	W8	W10	W12	W14	W16	W18a	W18b	W20	W22	W24a	W24b	
Visit Window (d)	NA	±5d	±5d	±5d	±5d	±5d	±5d	±5d	±5d	±5d	±5d	V11a + 7d	±5d	±5d	±5d	V14a + 10d	
Food Allergy & Anaphylaxis Emergency Care Plan	X																
Food Allergy Quality of Life Questionnaires ¹⁵		X									X				X		
PEESS or EEsAI Questionnaires		X		X						X					X		
Review Epinephrine Auto-injector ¹⁶		X	X	X	X	X	X	X	X	X	X	X	X	X	X	X	
Milk Protein OIT Dispensation ¹⁷				X	X	X	X	X	X	X	X ¹⁷		X	X	X ¹⁷		
Milk Protein OIT Administration				X	X	X	X	X	X	X			X	X			
Unused Milk Protein OIT Accountability ¹⁸					X	X	X	X	X	X			X	X	X	X	

1. V1 and associated procedures may take place over several visits/days; such visits do not need to be consecutive
2. V3 is only conducted for those receiving dupilumab or placebo for dupilumab every 2 weeks. Those receiving product every 4 weeks do not return to clinic for Visit 3.
3. V11b will be conducted within 7 days of V11a
4. V12 will be conducted two weeks after V11a, plus or minus 5 days
5. V14b will be conducted within 10 days of V14a
6. All screening procedures and results must be completed and obtained within the 6 months preceding V2, excluding milk-specific IgE. If milk-specific IgE results are needed to determine eligibility, such results must be from the 12 months preceding V2
7. Consent is to be obtained prior to conducting any screening or study procedure
8. When scheduled, these procedures are to be completed prior to study drug dosing (vital signs may additionally continue during and after dosing per protocol)
9. During DBPCFC, initial dose escalation, and any OIT updosing visit, vital signs will be collected every 15 minutes. Vital signs will additionally be taken prior to any dupilumab/placebo dosing and again prior to discharge or in-clinic OIT dosing following dupilumab/placebo dosing. At visits in which a participant will be dosed with 1000 mg and has tolerated the 1000 mg dose at the previous clinic visit, vital signs will be taken prior to dosing and again just prior to discharge at minimum.
10. Spirometry only conducted in those aged 7 years or older and able to perform spirometry reliably. Peak flow acceptable when spirometry unavailable; if both are unable to be performed, defer to clinician judgment
11. Both screening DBPCFCs may be completed in the same visit only if no adverse events occur during the first DBPCFC and time permits

12. At V1, screeners may undergo SPT to milk if no other SPT or milk-specific IgE result exists from the previous 6 or 12 months (for SPT or IgE, respectively) that meet eligibility criteria
13. When scheduled, blood draws include samples for mechanistic studies (including milk-specific and total IgE and IgG4, BAT, and other exploratory tests)
14. On days in which both the dupilumab/placebo and milk OIT are administered in clinic, the dupilumab/placebo will be administered at least 30 minutes before the milk OIT dose. Dupilumab/placebo may be given every 2 or 4 weeks; if given every 4 weeks, Visit 3 will not occur and no injection will be given at Visits 5, 7, and 9.
15. On days in which the Food Allergy Quality of Life Questionnaires are to be completed, the applicable versions of the questionnaire will be administered to the participant and guardian for completion as per investigator discretion; these forms may include those completed by the participant themselves (Child Form, Teenager Form, or Adult Form) and those completed by guardians of food-allergic children (Parent Form and/or Parental Burden Questionnaire).
16. Participant's will be asked to bring their current epinephrine auto-injector to each visit to ensure they are in possession of an auto-injector and that it is not expired. If needed, the participant will be provided with a prescription for a new epinephrine auto-injector.
17. The doses dispensed to the participant on V11a and 14a for home dosing will be the same dose level as the dose previously dispensed at V10 and 13, respectively. No dose escalation will occur at V11a or 14a.
18. Participants will return unused OIT doses from the home dosing kit dispensed at the previous visit. This accountability should be completed prior to the in-clinic OIT dosing; however, if the participant forgets to return the unused doses or inadvertently discards them, it is acceptable to assess dosing compliance solely through review of the Subject Dosing & Symptom Diary

9. STUDY VARIABLES

9.1. Demographic and Baseline Characteristics

Baseline characteristics will include standard demography (eg, age, race, weight, height, co-morbid atopic conditions, years with food allergy disease, sex, etc.), disease characteristics including medical history, and medication history for each subject.

9.2. Mechanistic Variables

Pharmacodynamic and biomarker variables of interest are:

- *Serum Milk-Specific and Total Antibody Assays (IgE, IgG4)*: The induction of milk-specific IgG4 during OIT has been reported in multiple studies. In some studies, milk-specific IgEs were seen to increase by ~3 fold after 3 months of OIT and gradually return to baseline at one year.
 - In dupilumab studies, dupilumab suppressed both total and allergen-specific IgEs. In general, dupilumab suppresses total IgE by ~ 50% with 12 to 16 weeks of treatment.
- *Basophil Activation Test*: Basophils are one cell type involved in acute allergic reaction. CD203c has been shown to be increased in basophils from milk allergic subjects compared to non-allergic healthy controls. The utility of the Basophil Activation Test (BAT) was assessed for diagnosing milk allergy in a well-characterized population of milk allergic, milk sensitized and non-sensitized children. The BAT showed high accuracy (97%) in diagnosing milk allergy. In a study of omalizumab in milk allergic subjects, CD203c expression in the BAT decreased during treatment and returned to pre-treatment levels after cessation of treatment ([Gernez 2011](#)). However, as a flow cytometry based test, the CD203c MFI reading is intrinsically highly variable. As an improvement to the traditional BAT, the basophil sensitivity test (BST) measures the minimum amount of milk extract required to activate basophils in subject whole blood, as measured by upregulation of CD203c. Basophil sensitivity to other allergens may also be tested.

9.3. Other Exploratory Research & Biospecimen Storage

Blood and esophageal tests may be obtained for additional exploratory tests such as whole blood stimulation and flow cytometry at baseline, 18 weeks, and 24 weeks. Biospecimen storage will occur in the [name] laboratory using a previously validated and published storage procedure for samples (available upon request).

10. COMPLETION AND STOPPING CRITERIA

10.1. Individual Subject Stopping Rules

Participants may be prematurely terminated from the study for the following reasons:

- The participant elects to withdraw consent from all future study activities, including follow-up
- The participant is “lost to follow-up” (i.e., no further follow-up is possible because attempts to reestablish contact with the participant have failed)
- The investigator no longer believes participation is in the best interest of the participant
- The participant dies
- Missing 2 consecutive doses of study drug (dupilumab or placebo)
- The participant does not tolerate 5 mg milk protein at the initial escalation (Visit 4)
- Missing ≥ 7 consecutive days of milk protein OIT therapy (e.g. concurrent illness such as gastroenteritis)
- Anaphylaxis resulting in hypotension, neurological compromise or mechanical ventilation secondary to OIT dosing or any food challenge
- The subject develops biopsy-documented eosinophilic esophagitis (EoE) with synchronous symptoms or other eosinophilic gastrointestinal disease
- Any serious or unexpected adverse event
- Any subject deemed to have severe allergic reactions and who receives aggressive therapy (e.g., mechanical ventilation, three or more doses of epinephrine for a life threatening reaction) at any time should be discontinued from further therapy
- Other circumstances including, but not limited to, the following:
 - Poor control or persistent activation of secondary atopic disease (e.g., AD, asthma)
 - Started on beta-blockers, or other prohibited medications, with no alternative medications per the prescribing clinician
 - Pregnancy

Subjects who are withdrawn prematurely from the study will be asked to complete study assessments, as described in **Section 8.5**.

10.2. Replacement of Subjects

Subjects prematurely discontinued from study will not be replaced.

10.3. Study Stopping Rules

During the course of the study, if the investigator or DSMB discover conditions that indicate that the study should be discontinued, an appropriate procedure for terminating the study will be instituted, including notification of the FDA and IRB or EC (ethics committee).

If any of the stopping rules listed below are met, study enrollment will be suspended, the initial dose day will be suspended, dose escalation during build-up will be paused, and all enrolled participants will remain on their current dose pending expedited review of all pertinent data:

- Any death related to dosing
- More than one participant requiring more than two injections of epinephrine during a single dupilumab injection

- One case of severe and prolonged anaphylaxis related to milk OIT dosing or oral food challenge that does not respond to 3 doses of epinephrine or that includes intubation
- More than 2 cases of hypotension related to milk OIT or oral food challenge
- More than 3 participants require more than 2 injections of epinephrine for anaphylaxis during a single dosing event of milk OIT
- More than 3 of either of the following events:
 - Severe adverse event, other than anaphylaxis, related to investigational product or
 - Eosinophilic esophagitis with clinical symptoms and confirmatory biopsy findings

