8. STUDY VISITS

8.1. Enrollment

The research study will be explained in lay terms to each potential research participant. The potential participant or guardian of a child participant will sign an informed consent form before undergoing any study procedures, with those aged 7 years or older completing an assent. Once the informed consent/assent has been signed, the participant is considered enrolled in the study. The purpose of enrollment is to complete the screening phase to determine eligibility. The participant will then be assigned a unique participant number after signing the informed consent/assent document(s).

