8.2. Screening/Baseline Visits (V1)

The purpose of the screening period is to confirm eligibility to continue in the study. After obtaining informed consent/assent, subjects will be assessed for eligibility at a screening visit. Procedures for the screening visit may be spread over one to three separate days; these days do not need to be consecutive and can be spread out over the course of the entire screening window. All assessments must be completed no more than 6 months preceding initiation dupilumab/placebo (Visit 2, week 0), excluding the milk-specific IgE value which may be taken from the previous 12 months if needed to establish eligibility. Baseline/screening visit procedures following requirements below but conducted under a different protocol within the past 6 months (or 12 months for milk-specific IgE) prior to Visit 2 can be used towards this study. Visit 1 may occur on the same day as Visit 2, but must be completed prior to any Visit 2 procedure taking place.

The following procedures, assessments, and laboratory measures will be conducted to determine participant eligibility and collect baseline data:

- Consent and assent (conducted prior to any screening or study procedure)
- Medical history, including review of all food allergies
- Physical assessment
- Documentation of con meds and AEs
- Epinephrine auto-injector training with Food Allergy & Anaphylaxis Emergency Care Plan
- SPT to cow's milk (only if needed to determine eligibility)
- Lung function (spirometry, or peak flow if spirometry not available, applicable, or able to be performed reliably by the participant). If spirometry and peak flow are both unable to be completed, defer to clinician judgment
- Urine pregnancy test in women of childbearing potential (WOCBP)

Any of the above items may be repeated within the 6 months preceding initiation of study treatment if warranted, in the opinion of the investigator, by changes in the subject's clinical status. After all other eligibility criteria have been met, DBPCFCs to a cumulative 444 mg of milk and placebo (oat)

Double-Blind Placebo-Controlled Food Challenge (DBPCFC) at Screening

Participants meeting all other eligibility criteria will undergo DBPCFC to cow's milk protein and oat (placebo) during screening to confirm an allergy to milk. Randomization of the placebo and

milk challenge order and preparation of the challenge materials will be performed by trained unblinded study personnel.

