Participants will receive their first dose of dupilumab/placebo in clinic at Visit 2. Participants will receive a second dose of dupilumab/placebo monotherapy at Visit 3 or 4, depending on dosing frequency determined by weight and age. Participants receiving dupilumab or placebo for dupilumab every 4 weeks will not return to clinic for Visit 3 as no dosing is scheduled at this time and associated procedures are not applicable.

Dupilumab and its matching placebo will be dosed according to the following algorithm:

- Participants aged 4-5 years old:
 - ≥ 5 to <15 kg will receive dupilumab 200 mg or placebo SC every 4 weeks following a loading dose of 400 mg on day 1 (Visit 2)
 - ≥ 15 to <30 kg will receive dupilumab 300 mg or placebo SC every 4 weeks following a loading dose of 600 mg on day 1 (Visit 2)
 - ≥ 30 kg will receive dupilumab 300 mg or placebo SC every 2 weeks following a loading dose of 600 mg on day 1 (Visit 2)
- Participants aged 6-17 years old:
 - ≥ 15 to <30 kg will receive dupilumab 300 mg or placebo SC every 4 weeks following a loading dose of 600 mg on day 1 (Visit 2)
 - ≥ 30 to <60 kg will receive dupilumab 200 mg or placebo SC every 2 weeks following a loading dose of 400 mg on day 1 (Visit 2)
 - ≥ 60 kg will receive dupilumab 300 mg or placebo SC every 2 weeks following a loading dose of 600 mg on day 1 (Visit 2)

- Participants aged 18 years or older will receive dupilumab 300 mg of placebo SC every 2 weeks following a loading dose of 600 mg on day 1 (Visit 2)

Prior to the first dose of study drug at Visit 2, participants will undergo blood draw and provide a stool/saliva sample (optional). Participants will be monitored for at least 30 minutes following each dose of dupilumab/placebo. Vital signs will be taken prior to dosing and again prior to discharge. Prior to the completion of Visit 2, participants will be trained on a Daily Dosing & Symptom Diary. Participants will be asked to bring their epinephrine auto-injector to each visit throughout the study in order to confirm they are equipped with an injector and that it is not expired. Participants with no injector or an injector that is expired or expiring prior to the next clinic visit will be provided with a prescription for a new epinephrine auto-injector.

Combination Therapy Phase (Visit 4 to Visit 10, Weeks 4 to 16)

Initial Dose Escalation Day (Visit 4, Week 4)

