12.2. Study Monitoring Plan

The investigators will work with the independent DSMB. The DSMB will meet every 6-12 months, or earlier if needed, to review safety data including all reported AEs and SAEs, as well as major and non-major deviations.

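### A single non-fatal, treatment-refractory or intubated anaphylaxis pauses the trial if related to milk, but meets no listed stopping rule if attributed only to the dupilumab/placebo injection

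*Combined protocol and SAP*

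**What the plan says.** Section 10.3 lists events that pause the study pending expedited review, and the synopsis repeats the list. Three bullets bear on a severe allergic reaction to the injection:

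- A one-case rule: "One case of severe and prolonged anaphylaxis related to milk OIT dosing or oral food challenge", qualified by failure to respond to three epinephrine doses or by intubation. It names no other source of the reaction.
- An injection rule: "More than one participant requiring more than two injections of epinephrine during a single dupilumab injection".
- A rule needing more than three events of this kind: "Severe adverse event, other than anaphylaxis, related to investigational product".

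When a rule is met, "study enrollment will be suspended, the initial dose day will be suspended, dose escalation during build-up will be paused", and participants already in the study stay on their current dose.

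The protocol foresees anaphylaxis to the drug. Section 5.2 lists it among the rare risks of dupilumab, and section 11.2.5 makes life-threatening anaphylaxis an event of special interest for dupilumab/placebo. Section 8.3 states: "Participants will receive their first dose of dupilumab/placebo in clinic at Visit 2". That visit carries the loading dose, and milk OIT does not begin until Visit 4.

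**The concern.** The rules are strictest for milk at the severe end and silent for the injection at the same point. An intubation or a refractory reaction is the kind of event for which a mandatory pause is written, so that the decision does not depend on someone's judgement on the day. Injection-only attribution is a realistic outcome. No milk OIT or follow-up challenge is scheduled at Visits 2 and 3. From Visit 4 to Visit 10, section 1.2.3.1 requires the injection at least 30 minutes before in-clinic milk, so that events can be attributed to one or the other. The participants include children from age 4. After one such case, the plan as written would require no pause.

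**Working it through.** The plan gives no operating figure for its stopping rules, so there is none to reproduce. The check has three parts.

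**1. Each 10.3 trigger applied to one non-fatal anaphylaxis with intubation or no response to three doses**

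| Trigger | Related to milk | Attributed only to injection |
|---|---|---|
| Death related to dosing | not met | not met |
| Injection rule (more than 1 participant, each with more than 2 epinephrine injections) | does not apply | not met: one participant |
| One-case severe and prolonged anaphylaxis | **met** | not met: milk or challenge only |
| More than 2 hypotension cases | not met by one case | does not apply: milk or challenge only |
| More than 3 participants with more than 2 epinephrine injections | not met by one case | does not apply: milk OIT only |
| More than 3 severe events related to product | excluded: anaphylaxis | excluded: anaphylaxis |
| More than 3 cases of eosinophilic esophagitis | does not apply | does not apply |

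With two injection-only cases, the injection rule is met only if each needed more than two epinephrine injections. Intubated injection-only cases treated with two or fewer epinephrine doses meet no listed trigger at one, two or four cases.

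**2. Where the gap lies**

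Participants on four-weekly dosing have one injection visit with no milk OIT scheduled (Visit 2). Those on two-weekly dosing have two (Visits 2 and 3). With 58 in the dupilumab arm (section 13.2), that is 58 × 1 = 58 to 58 × 2 = 116 visits before dropout. This counts visits and is not a measure of risk. At later injection visits the gap is the interval before milk is given. After that, a reaction judged even possibly related to milk counts as related under Table 6 in section 11.3.2, and the one-case rule applies.

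**3. What the wider rule would add**

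All risks here are assumptions. Let r be the risk per participant of an injection-only case not responding to three doses, and q the risk of needing more than two epinephrine injections after a study injection, with q ≥ r. Take n = 58 and ignore the placebo arm. The existing rule fires with two or more participants of type q. The wider rule adds a pause when exactly one participant is of type q and that one is a non-response case:

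added chance = 58 × r × (1 − q)^57

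- r = 0.01%, q = r: 58 × 0.0001 × 0.9999^57 = 0.58 points. With q = 3r: 0.57 points.
- r = 0.1%, q = r: 58 × 0.001 × 0.999^57 = 5.48 points. With q = 3r: 4.89 points.

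The existing rule fires with probability 0.16% at q = 0.1% and 1.33% at q = 0.3%. If r = q = 0.5%, the chance of at least one case is 25.2%, against 3.4% for at least two, so the added chance is 25.2 − 3.4 = 21.8 points. Intubated cases treated with two or fewer epinephrine doses are not in this model and would add to it.

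**The case against.** The strongest reply is that the plan does not leave such an event unattended. Section 10.3 opens with a clause letting the investigator or DSMB act on any concerning condition. Sections 6.5.2 and 10.1 provide for stopping treatment in the affected participant. Section 11.5 requires reporting to the sponsor within 24 hours, section 12.5 lets the sponsor stop the study for safety, and section 5.8.1 lets the DSMB see the allocation. On epinephrine count alone the injection rule is stricter than the milk rule (more than 1 participant against more than 3). Separate thresholds may also be deliberate for a drug already approved in other indications. All of this stands, and it makes the gap narrow. None of it mandates a pause, and the documents give no reason for treating the most severe presentation more leniently when the injection is the cause.

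A reader might infer two stronger points, which the documents do not support.

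- *That a newly randomised participant would complete all injections before anyone reviews the case.* Section 12.2 says "The DSMB will meet every 6-12 months, or earlier if needed", and the inference would need a 24-hour report of an intubation or refractory reaction to prompt no action at all.
- *That suspending enrollment would leave new loading doses running.* Section 8.1 does say "Once the informed consent/assent has been signed, the participant is considered enrolled in the study", which precedes randomisation. But sections 3.3, 13.2 and 13.8 use the word for participants in the randomised arms, and on that reading new loading doses already stop. The wording is open to two readings and is not a separate defect.

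**Conclusion.** The point holds in a limited form. One non-fatal, severe and prolonged anaphylaxis with intubation or no response to three epinephrine doses pauses the trial if related to milk OIT or a food challenge. It meets no listed trigger if attributed only to the dupilumab/placebo injection. This follows from the wording of 10.3 and the synopsis and rests on no assumed rate.

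The consequence is that a pause is left to discretion; action is not ruled out. The chance of such an event cannot be estimated from the documents. Section 5.2 places anaphylaxis only within a group of risks with incidence below 1%. The 0.6 to 5.5 point range therefore illustrates the cost of the wider rule under assumed risks. It should not be read as a ceiling, because it omits intubation cases and grows with the assumed risk. The change is a cheap improvement worth making.

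**What to change.** In section 10.3 and in the synopsis, insert *dupilumab/placebo injection,* directly after *related to* in the one-case bullet. Keep milk OIT dosing, oral food challenge and the qualifiers on three epinephrine doses and intubation. Leave the two-participant epinephrine rule, the hypotension rule and all other counts as they are.

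An optional clarification is to state that, for an injection-related trigger, suspending enrollment includes randomisation and the Visit 2 loading dose. Holding only participants not yet dosed causes no missed doses under the rule in 10.1 on two consecutive missed doses. Neither change stops injections in those already past Visit 2; that decision stays with the expedited review.

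The cost is a few words in two places by amendment, with no new data. The downsides are the somewhat higher chance of a temporary pause and possible repeat screening after a long one, since section 8.2 says "All assessments must be completed no more than 6 months preceding initiation dupilumab/placebo", with an exception for milk-specific IgE.
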